6.0 STATISTICAL CONSIDERATIONS

6.1 Overview of study design

This is a phase I/II clinical trial designed to first determine the MTD of the combination of CT-011 + lenalidomide in relapsed/refractory MM patients and then to assess the associated efficacy of this regimen in this patient population through evaluation of the overall response rate. The phase I portion follows the standard cohorts-of-3 phase I clinical trial design, and the phase II portion will utilize a one-stage three outcome phase II design (Sargent et al, 2001).

6.1.1 *Phase I portion*

In the phase I portion, we will assess the MTD using a standard cohorts-of-3 phase I trial design, where the MTD is defined as the dose level at which no more than one of 6 patients experiences a dose-limiting toxicity (DLT). The dose escalation rules follow the standard design, where cohorts of 3 are accrued to a dose level and evaluated for DLT before making a decision to dose escalate or not. If in the first 3 patients on a dose level there are no DLTs observed, the next cohort of 3 can be accrued to the next dose level. If one DLT of the first 3 patients at a dose level experiences DLT, then 3 additional patients will be accrued to that dose level to ensure it is tolerable and does not exceed the MTD. Any dose that has two or more patients with DLTs has exceeded the MTD and is deemed to have unacceptable toxicity. If the first dose level proves to have unacceptable toxicity (i.e. 2+ DLTs), then 3-6 patients will be accrued to the de-escalation dose level (dose level -1). For this portion of the trial, we expect a minimum of 12 patients (worst case scenario of 2+ DLTs on dose level cohorts 1, -1, and -2) and a maximum of 30 patients (e.g. 6 at each of the 4 dose levels and an intermediate dose level). Adverse events and toxicities will be summarized using the NCI CTCAE version 4 and based on severity and perceived attribution to study treatment; these outcomes will be assessed and tabulated by dose level.

6.1.2 *Phase II portion*

Previous studies of lenalidomide alone in a similarly defined relapsed/refractory MM patient population has shown an overall response rate of 25%, which also included the addition of dexamethasone after 2 cycles to non-responding stable disease patients. We will consider this regimen promising if the true overall response rate is 50% or greater when lenalidomide is combined upfront with CT-011. Therefore, we will test the null hypothesis that the true overall response rate (ORR) is at most 25% (reflecting a combination regimen ORR that would not be of interest) versus our alternative hypothesis that the true ORR in patients treated with this combination regimen is at least 50%.

Decision Rule: The largest response rate where this treatment regimen would be considered ineffective in this population is 25%, and the smallest response rate that would warrant subsequent studies with this proposed regimen in this patient population is 50%. The following Three-Outcome phase II study design is a modification of the standard one-stage phase II design and uses a maximum of 29 evaluable patients to test the null hypothesis that the true response rate is at most 25%. Since we will include the 6 patients treated at the MTD from the phase I portion of the trial, this will require accruing an additional 23 evaluable patients for this phase of the study. Based on this study design, there are three possible outcomes:

- **Not promising**: This regimen will be classified as not promising with respect to the response rate in this patient population if at most 9 patients have any response after 4 cycles of therapy out of the total 29 evaluable patients.
- **Promising**: This regimen will be classified as promising with respect to increasing the response rate in this patient population if at least 12 patients have an observed response to treatment after 4 cycles of therapy out of the total 29 evaluable patients. Subsequent larger confirmatory studies may be warranted.
- **Inconclusive**: The results of this study will be classified as inconclusive with respect to this regimen demonstrating an improved response rate if only 10 or 11 of the 29 total evaluable patients have a response after 4 cycles of therapy. In this case, other factors such as progression-free survival, toxicity, and correlative outcomes will be used in addition to the response data to make the final determination as to whether or not this treatment is considered promising and worthy of further study in this patient population.

In this type of three-outcome phase II design with an uncertainty region, the associated errors are not the same as in the standard phase II study designs. In this study, the type I and type II error rates are constrained at 4% and 3%, respectively; The other parameters included in this type of design are eta (the probability of determining that a regimen is not worth pursuing further when it truly is not effective) and pi (the probability of determining that a regimen is promising when it truly is). Under this design, eta=0.83 and pi=0.87.

The proportion of responses (partial and complete) will be calculated out of all eligible patients who receive any treatment in that disease group who are included in the phase II assessment. Assuming the number of responses is binomially distributed, 95% binomial confidence intervals will also be calculated for the estimate of the proportion of responses. All adverse events will be summarized by the NCI CTCAE v. 4 criteria, and tabulated across all patients who received any treatment with a focus on severe (grade 3+) adverse events and toxicities (i.e. those deemed at least possibly related to study treatment). In addition, we will summarize the proportion of patients who received dexamethasone after being stable disease but without response after 2 cycles of therapy. We will descriptively summarize how many of these patients were converted to response after the addition of dexamethasone. Since the addition of dexamethasone is part of the overall treatment regimen that is dependent on treatment outcome at a certain time point, we will not make other adjustments to the study design to evaluate these patients separately outside of this descriptive summarization of whether or not they received the dexamethasone. We will evaluate other clinical outcomes such as progression-free survival and overall survival using the methods of Kaplan-Meier, although these analyses will be exploratory and primarily to help describe the cohort itself.

Correlative analyses will also be done, including analysis of markers of the immunogenicity of CT-011. In particular, we will evaluate biological and cellular markers in patients treated with CT-011, measure PD-L1 expression on MM cells, percentage increase in NK cell activity, migration, immune complex formation, and cytotoxicity. Other markers such as plasma cell IHC baseline expression to characterize immunologic markers of MM cells that are responsive to CT-011 such as TNF-alpha, IFN-gamma, CD4, CD8, and granzyme B will be evaluated in addition to markers of MM cells responsive to lenalidomide (Spars, IRF-4). Changes in these markers before and after therapy will be explored using graphical analyses as well as summarized quantitatively. We will also explore how changes in these correlative markers may differ based on whether or not the patient achieved a response or not; to accomplish this, we will utilize different plotting characters and colors for successes vs. not in the graphical analyses to help identify potential patterns, and summarize the changes quantitatively between successes vs. not. Given the total sample size available, we expect

that these analyses will be exploratory at best, but will provide important insights into mechanisms of action and vital preliminary data for future studies and hypothesis generation.

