the earliest of the following events: disease progression, the time of initiation of new therapy, death or study completion.

Study completion is defined as 30 days after the last subject remaining on study medication discontinues study medication.

For the Phase II portion

Upon completion of the cohorts in phase I, the phase II portion of the study will commence utilizing the planned target doses (or MTDs determined) with CT-011 in combination with lenalidomide and dexamethasone

During the phase II portion of this trial, we will not evaluate patients for DLTs as was done in the phase I portion; however, we will use the DLT criteria to identify potential toxicity and tolerability concerns occurring at any cycle to initiate further evaluation to ensure safety of patients. An independent Data Monitoring Committee will continue oversight of this trial.

Treatment will continue until Progression of disease, death, unacceptable toxicity or patient or treating physician decision to discontinue therapy.

Dosing Regimen

Dosing cohorts for the phase I study: We will conduct a standard 3+3 design over 4 dose levels of 1.5, 3, 3, and 6 mg/kg of CT-011 given intravenously every 4 weeks (28 days) on day 3, and lenalidomide given at 15, 15, 25, and 25 mg orally daily on days 1-21 of a 28-day cycle. The study drug CT-011 and lenalidomide can move independently of one another as described in the Table below. Dexamethasone 40 mg orally weekly may be added if only stable disease after 3 cycles according to the IMWG response criteria (section 13-0). Dexamethasone can be reduced to 20 mg based on tolerability or if patient is 70 years or older.

A minimum of 3 patients to a cohort with at least one week break between cohorts.

	CT-011- mg/kg day 3
Cohort -1	1.5
Cohort -2	1.5
Cohort 1	1.5
Cohort 2	3
Cohort 3	3
Cohort 4	6

	Lenalidomide- mg Days 1-21
Cohort -1	10
Cohort -2	5
Cohort 1	15
Cohort 2	15
Cohort 3	25
Cohort 4	25

If a DLT occurs in 2 or more patients during the first cycle, we will consider this

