4.3 Dose Escalation/De-escalation

If a DLT occurs in 2 or more patients on a dose level during the first cycle, the MTD will be exceeded and we will consider this dose level to be intolerable. If a DLT occurs in 1 of 3 patients during this time, an additional 3 patients will be enrolled at that dose level cohort and evaluated for DLT before dose escalation can proceed. If no other patient in the cohort has a DLT, escalation to the next cohort may proceed 1 week later from the last included patient on the current cohort. If a second patient in a cohort has a DLT, MTD determination will then be conducted by one of the following schemes:

- If ≥ 2 of 3 patients in cohort 1 exhibit a DLT at the dose of 1.5 mg/kg CT-011 in combination with lenalidomide 15 mg, 3 more patients will be enrolled at a de-escalated dose level cohort. This de-escalation cohort (Cohort -1) will use the same dose of CT-011 (1.5 mg/kg) in combination with 10 mg lenalidomide. If no further DLTs are observed, we will consider dose escalation of the CT-011 with this lower dose of lenalidomide such that the dose escalation of CT-011 to 3 mg/kg with lenalidomide 10 mg will proceed in the next cohort. However, if ≥ 2 patients experience DLT with CT-011 1.5 mg/kg and lenalidomide 10 mg, then we will further de-escalate lenalidomide to 5 mg and enroll 3 more patients on CT-011 1.5 mg/kg combined with lenalidomide 5 mg. The same criteria for MTD will be used for these de-escalation dose level cohorts.
- If ≥ 2 patients in cohort 2 exhibit a DLT at the dose of 3 mg/kg CT-011 in combination with lenalidomide 15 mg, we will explore tolerability of an intermediate dose level of lenalidomide, where 3 patients will be enrolled and treated with 3 mg/kg of CT-011 in combination with 10 mg lenalidomide. The dose escalation of CT-011 to 6 mg/kg with lenalidomide 10 mg will proceed in the next cohort if no more than one DLT is observed in the 3 mg/kg CT-011+10mg lenalidomide cohort.
- If ≥ 2 patients in cohort 3 exhibit a DLT at the dose of 3 mg/kg CT-011 in combination with lenalidomide 25 mg, 3 more patients will be enrolled at the 3 mg dose of CT-011 in combination with 15 mg lenalidomide. If there is < 1 DLT with CT011 3mg/kg and lenalidomide 15 mg, this will be defined as the MTD. If there are 2 or more DLT, then 3 additional patients will be enrolled at the CT-011 3mg/kg and lenalidomide 10 mg, which will become the MTD.

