- If ≥ 2 patients in cohort 4 exhibit a DLT at the dose of 6 mg/kg CT-011 in combination with lenalidomide 25 mg, 3 more patients will be enrolled at the 6 mg dose of CT-011 in combination with 15 mg lenalidomide. If there is < 1 DLT with CT011 6mg/kg and lenalidomide 15 mg, this will be defined as the MTD. If there are 2 or more DLT, then 3 additional patients will be enrolled at the CT-011 6mg/kg and lenalidomide 10 mg, which will become the MTD

To determine dose escalation, we will focus on the number of patients who experience dose limiting toxicity; i.e. a patient who experiences more than one DLT will be counted only once.

Discontinuation of treatment due to disease progression will not constitute a DLT.

In the Phase 1 portion of the study, subjects who withdraw or prematurely discontinue treatment before completing the first treatment cycle for reasons other than toxicity and DLT will be replaced.

After 4 cycles of therapy or earlier if clinically indicated, response determination will be assessed by the IMWG criteria. At the end of Cycle 4, if a subject has responded (complete or partial response) or has stable disease, dosing with CT-011, lenalidomide and dexamethasone(if initiated after cycle 1-2) will continue for a minimum of 8 additional cycles or until withdrawal.

For the Phase II portion

Upon determination of the MTD in the phase I portion of this trial, the phase II portion of the study will commence enrollment at the MTD determined in the phase I portion with CT-011 in combination with lenalidomide. In the event that a MTD is not established, safety and tolerability data collected in the Phase I portion of the study will guide decisions on dosing of CT-011 in the phase II trial.

Dexamethasone 40 mg orally weekly may be added if only stable disease after 3 cycles according to the IMWG criteria (section13). Dexamethasone can be reduced to 20 mg based on tolerability or if patient is 70 years or older.

During the phase II portion of this trial, we will not evaluate patients for DLTs as was done in the phase I portion; however, we will use the DLT criteria to identify potential toxicity and tolerability concerns occurring at any cycle to initiate further evaluation to ensure safety of patients. An independent Data and Safety Monitoring Committee will continue oversight of this trial. See Appendix E for details.

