4.5 Study Accrual

For the phase I portion, a minimum of 12 and a maximum of 30 patients will be recruited. Once the MTD has been established, an additional 23 subjects will be treated at the MTD in the phase II.

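### The phase I minimum of 12 does not match the worst case given for it (9 patients at the least), and the maximum of 30 holds only if the fallback levels after cohort 4 never expand

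*Combined protocol and SAP*

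**What the plan says.** Section 6.1.1 gives both ends of the phase I range with a reason for each. For the lower end: "we expect a minimum of 12 patients (worst case scenario of 2+ DLTs on dose level cohorts 1, -1, and -2". For the upper end: "a maximum of 30 patients (e.g. 6 at each of the 4 dose levels and an intermediate dose level". Section 4.5 repeats the range as a recruitment statement without the reasons: "For the phase I portion, a minimum of 12 and a maximum of 30 patients will be recruited". The synopsis, section 2.1 and section 5 carry the same figures.

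The rules that should generate these figures are as follows.

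- **Cohort size.** The synopsis (Dosing Regimen) sets the smallest cohort: "A minimum of 3 patients to a cohort with at least one week break between cohorts".
- **Expansion.** Section 4.3: "If a DLT occurs in 1 of 3 patients during this time, an additional 3 patients will be enrolled at that dose level cohort".
- **Failure of a level.** Sections 4.3 and 6.1.1 treat a level with two or more patients with DLTs as exceeding the MTD.
- **MTD definition.** Sections 2.3 and 6.1.1 define it on six patients, with at most one DLT among them. Sections 5 and 6.1.2 carry the six patients treated at the MTD into phase II.
- **Fallback after cohort 4.** Section 4.3 opens a first fallback level (6 mg/kg with lenalidomide 15 mg) with 3 patients. If two or more DLTs occur there, "then 3 additional patients will be enrolled at the CT-011 6mg/kg and lenalidomide 10 mg, which will become the MTD".
- **Replacement.** Section 4.3 replaces phase I patients who leave before completing cycle 1 for reasons other than toxicity. No number is given.

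**The concern.** The two figures should follow from the escalation rules, and the reasons given for them do not lead there. The lower figure is attached to a scenario that can end with fewer patients. The upper figure is illustrated with one intermediate level, whereas section 4.3 allows two in sequence after cohort 4.

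The upper figure matters more. Outside section 6.1.1 it is stated as the maximum that will be recruited. If the rules can pass it, the study could use up its stated accrual before the second fallback level opens. The plan does not say what happens then.

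**Working it through.** **Possible outcomes at one level.** Under the 3+3 rules a level ends in one of four ways:

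- 0 of 3 with a DLT: tolerated, 3 patients.
- 1 of 3, then no further DLT: tolerated, 6 patients.
- At least 2 of the first 3: failed, 3 patients.
- 1 of 3, then at least one more: failed, 6 patients.

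**Minimum.** The named scenario is failure at cohorts 1, -1 and -2. Each uses 3 or 6 patients:

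| Cohorts expanded before failing | Total |
|---|---|
| none | 3 + 3 + 3 = 9 |
| one | 6 + 3 + 3 = 12 |
| two | 6 + 6 + 3 = 15 |
| all three | 6 + 6 + 6 = 18 |

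The plan's 12 appears here only if exactly one cohort expands, so it is not the minimum of the scenario. Enumerating every path with 3 or 6 patients per level also gives 9 as the smallest total. Twelve does arise as 4 × 3, four levels with no DLT. If the six MTD patients that phase II carries forward must all come from phase I, that path becomes 3 + 3 + 3 + 6 = 15.

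**Maximum.** The plan's own count is reproduced: 4 × 6 + 6 = 5 × 6 = 30. The longest path by the cohort that fails, with every level at 6, is:

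| Failing cohort | Levels used | Total |
|---|---|---|
| 1 | 1, -1, -2 | 18 |
| 2 | two main, two further | 24 |
| 3 | three main, two fallback | 30 |
| 4 | four main, two fallback | 36 |

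Only the cohort 4 path can pass 30. The four main levels use 24 (cohorts 1 to 3 at 1 of 6 each, cohort 4 failing at 6). The rest depends on how the fallback levels are filled:

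| First fallback | Second fallback | Total |
|---|---|---|
| 3 | 3 | 24 + 3 + 3 = 30 |
| 3 | 6 (filled to the MTD definition) | 24 + 3 + 6 = 33 |
| 6 (expanded, then failed) | 3 | 24 + 6 + 3 = 33 |
| 6 | 6 | 24 + 6 + 6 = 36 |

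Against 30, these are excesses of 3/30 = 10% and 6/30 = 20%. Replacements would be added to any of them.

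**How likely is an overrun?** The documents give no DLT rates, so only an upper bound is possible. The DLT probability is chosen separately at each level to make a total above 30 as likely as possible. With the second fallback level held at 3, every earlier level must expand:

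- Expanded and tolerated: 3p(1−p)^5, largest at p = 1/6, where it is 0.201.
- Expanded and failed: 3p(1−p)^2 × [1 − (1−p)^3], largest near p = 0.43, where it is 0.341.
- Bound: 0.201^3 × 0.341^2 = 0.0009, about 0.1%.

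The same maximisation gives about 0.6% if the second fallback level expands by the 1-of-3 rule, and about 1.2% if it is always filled to six. These are ceilings, not estimates.

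**The case against.** The best defence of 30 is the literal text of section 4.3. It assigns 3 patients to each fallback level, and 24 + 3 + 3 = 30. The illustration in section 6.1.1 is introduced as an example, and its different count also gives 30. This defence stands far enough that 30 cannot be called wrong outright. A reader might infer that the rules reach 33 to 36 without condition; the documents do not settle that.

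The literal reading is not comfortable, however. The section 6.1.1 example counts six, not three, at the intermediate level. The cohort 4 fallback text covers fewer than one DLT and two or more, but not exactly one, and the only rule in the plan for that case is the general one that enrols 3 more. The MTD is defined on six patients.

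A reader might also infer that phase I would end without an MTD once 30 is reached. The documents do not support that. Section 4.3 names the last fallback level as the MTD. It also says that phase I safety data will guide phase II dosing if no MTD is established. The synopsis separately names the level immediately below a level with 2 DLTs in 6.

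On the minimum, it is fair to say that no test or stopping rule uses the figure, and that 12 is a possible total of the named scenario. It is still not the minimum of that scenario. The figure of 15 is an inference: no sentence in sections 4.3 or 6.1.1 orders three more patients at cohort 4 after 0 of 3.

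**Conclusion.** The minimum is wrong for the reason given, whichever way the fallback rules are read: the named scenario needs at least 9 patients, 3 fewer than stated. This rests only on cohorts of 3 and failure at two DLTs.

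The maximum is conditional. Thirty holds if both fallback levels after cohort 4 stay at 3. It becomes 33 or 36 evaluable patients if the expansion rule, the six-patient MTD definition, or both apply to them, as the section 6.1.1 example implies. Exceeding 30 has a probability of at most about 1.2% under the least favourable reading and DLT rates.

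The consequence is limited to accrual planning and the consistency of the stated ceiling. The 29-patient phase II decision rule and its error rates do not depend on it.

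**What to change.** 1. In section 6.1.1, give 9 as the minimum for failure at cohorts 1, -1 and -2, and remove the worst-case label from 12. If 12 is kept, describe it as four levels of 3 with no DLT, and say whether the six MTD patients for phase II must all come from phase I (15 on that path). Where the range is repeated, make the lower figure agree.
2. Reconcile sections 4.3 and 6.1.1 on whether the fallback levels expand, including when exactly one DLT occurs. Which rule applies is for the study team to decide; none is proposed here.
3. Restate the maximum to match in the synopsis and sections 2.1, 4.5, 5 and 6.1.1: 30 if fallback levels do not expand, 33 or 36 if they do, with replacements stated as additional. Alternatively, label 30 a recruitment cap and state what happens if it is reached.

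The cost is a protocol amendment and possibly a slightly less favourable ceiling. Step 2 is more than wording, because the maximum cannot be fixed until the expansion question is settled.

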1.3.1 Clinical Experience in Relapsed Multiple Myeloma

A multicenter, open-label, randomized phase 2 study evaluated 2 doses of lenalidomide for relapsed, refractory multiple myeloma patients. Seventy patients were randomized to receive oral lenalidomide either 30 mg once-daily or 15 mg twice-daily for 21 days of every 28-day cycle. Patients with progressive or stable disease after 2 cycles received dexamethasone. Analysis showed an increased

grade 3/4 myelosuppression in patients receiving 15 mg twice daily as compared to those receiving 30mg daily (41% versus 13%, $P = .03$). Responses were evaluated according to European Group for Blood and Marrow Transplantation (EBMT) criteria. Overall response rate (complete, partial, or minor) to lenalidomide alone was 25% (24% for once daily and 29% for twice-daily lenalidomide). Median overall survival (OS) in the 30-mg once-daily and twice-daily groups was 28 and 27 months, respectively. Median progression free survival was 7.7 months on once-daily versus 3.9 months on twice-daily lenalidomide ($P = 0.2$). Dexamethasone was added in 68 patients and 29% responded. Time to first occurrence of clinically significant grade 3 / 4 myelosuppression was shorter in the twice daily group (1.8 vs 5.5 months, $P = .05$). Significant peripheral neuropathy and deep vein thrombosis each occurred in only 3%. Lenalidomide was active and well tolerated in relapsed, refractory myeloma, with the 30-mg once-daily regimen providing the basis for future studies as monotherapy and with dexamethasone³².

In a safety and efficacy study of single agent lenalidomide in relapsed and refractory multiple myeloma patients, lenalidomide 30 mg (days 1-21 of 28 day cycle) was given to 222 patients who had relapsed or progressed after 1 or more prior therapies³³. Sixty-seven percent of patients had had three or more prior therapies, and 45% had had one or more autologous stem cell transplants. Eighty and 43% of patients had had thalidomide and bortezomib based therapies respectively. The median dose of lenalidomide was 25 mg (5-30mg) and the median duration of treatment was 4.2 months (0.06-38). The overall response rate (complete and partial) was 26% with 2% complete response³³.

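### Section 6.1.2 says the 25% behind the null included add-on dexamethasone, 1.3.1 gives it for lenalidomide alone, and 6.3 counts stable disease as response: the benchmark and response definition need reconciling

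*Combined protocol and SAP*

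**What the plan says.** **Benchmark and rule (6.1.2).** The opening sentence refers to previous studies of lenalidomide alone and says the evidence "has shown an overall response rate of 25%, which also included the addition of dexamethasone after 2 cycles to non-responding stable disease patients". The null is a true response rate of at most 25%, described as "reflecting a combination regimen ORR that would not be of interest"; the alternative is 50%. With 29 evaluable patients, at most 9 responders after 4 cycles is *not promising*, 10 or 11 is *inconclusive*, and 12 or more is *promising*. The stated type I and II errors are 4% and 3%, with eta 0.83 and pi 0.87.

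**What is counted (6.1.2).** "The proportion of responses (partial and complete) will be calculated out of all eligible patients who receive any treatment". The plan will describe how many patients "received dexamethasone after being stable disease but without response after 2 cycles of therapy" and how many then converted to response. Beyond that, because dexamethasone is regarded as part of the regimen, "we will not make other adjustments to the study design to evaluate these patients separately".

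**The historical data (1.3.1).** For the randomized phase 2 study of 70 patients: "Overall response rate (complete, partial, or minor) to lenalidomide alone was 25% (24% for once daily and 29% for twice-daily lenalidomide)". Patients with progressive or stable disease after 2 cycles went on to dexamethasone, and that step is reported on its own: "Dexamethasone was added in 68 patients and 29% responded". For the 222-patient single-agent study: "The overall response rate (complete and partial) was 26% with 2% complete response". No dexamethasone step is described there.

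**Response definition elsewhere.** Section 6.3 includes stable disease in the response rate and divides by per protocol patients. Appendix B, note e, advises against using stable disease as an indicator of response. Appendix B has no minor-response category.

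**The concern.** A single-arm go/no-go rule means only as much as its benchmark. On the natural reading of 6.1.2, the 25% already absorbs the effect of delayed dexamethasone. A reader would then take 4% as the chance of wrongly calling the combination *promising* when CT-011 adds nothing to lenalidomide with optional dexamethasone. Section 1.3.1 does not support that reading, because its 25% excludes the dexamethasone step and includes minor responses, which the primary analysis does not count.

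A second problem sits in 6.3. If its response rate were put through the 29-patient rule, the 25% null would be compared with a quantity that it was never meant to describe.

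**Working it through.** **1. Reproduce the stated figures.** Inputs from 6.1.2: n = 29, cut-offs 9 and 12, p0 = 0.25, p1 = 0.50. With X ~ Binomial(29, p), P(X ≥ 12) = Σ C(29,k) p^k (1−p)^(29−k) over k = 12 to 29, and P(X ≤ 9) is the same sum over k = 0 to 9.

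- Type I error: P(X ≥ 12 | 0.25) = 0.0390 (stated 4%)
- Type II error: P(X ≤ 9 | 0.50) = 0.0307 (stated 3%)
- eta: P(X ≤ 9 | 0.25) = 0.8337 (stated 0.83)
- pi: P(X ≥ 12 | 0.50) = 0.8675 (stated 0.87)

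All four agree after rounding.

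**2. What the 4% covers.** P(X ≥ 12) rises with p, so 0.039 is its maximum over the whole null. It is 0.007 at 20% and 0.029 at 24%. Likewise eta is at least 0.83 for any rate up to 25%.

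**3. Is any documented rate like-for-like?** The rate needed is complete plus partial response, after 4 cycles, to lenalidomide with delayed optional dexamethasone.

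| Source | Rate | Responses counted | Dexamethasone |
|---|---|---|---|
| 1.3.1, 70-patient study | 25% | complete, partial, minor | not included |
| 1.3.1, same study, second step | 29% of 68 | not specified | added for progressive or stable disease |
| 1.3.1, 222-patient study | 26% | complete, partial | none described |
| Table 1-1, phase III studies | 61%, 60.2% | overall response | high dose from the start |

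None matches. The 26% comes nearest, since it matches on response categories.

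**4. Can the first two rows be combined?** Not reliably. 25% of 70 is 17.5, so 17 or 18 responders (17/70 = 24%, 18/70 = 26%). That leaves 53 or 52 non-responders, yet 68 patients are said to have received dexamethasone. A different denominator or later use could explain this, but the document does not say.

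**5. The unchanged rule above 25%.** The rates are assumptions about the background regimen; 26% is documented, but for lenalidomide alone.

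| True rate | P(*promising*) | P(*not promising*) |
|---|---|---|
| 25% | 0.039 | 0.83 |
| 26% | 0.051 | 0.80 |
| 30% | 0.129 | 0.64 |
| 35% | 0.295 | 0.41 |

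**6. Direction.** Dropping minor responses lowers the benchmark, and adding dexamethasone conversions raises it. With assumed values, removing 5 points of minor response and converting 10% of the rest gives 0.20 + 0.80 × 0.10 = 28% (risk 0.084). Removing 10 points with the same conversion gives 0.15 + 0.85 × 0.10 = 23.5% (risk 0.025). The sign cannot be settled from the document.

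**7. Stable disease.** Suppose 25% respond and a further 25% have stable disease (the second figure is an assumption). The 6.3 rate would be 50%, and the rule would return *promising* with probability 0.87 for a regimen at the null response rate.

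**The case against.** **The sentence is ambiguous.** It begins with studies of lenalidomide alone, so the dexamethasone clause may describe how those studies were run rather than what the 25% counts. That is a fair reading. It is a reason to clarify the sentence, because the other reading is at least as natural and changes what the null represents. Nor can 1.3.1 simply be taken as correct, given its own awkward count of 68.

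**25% is a threshold, and the null is composite.** This stands. Section 6.1.2 calls 25% the largest rate regarded as ineffective, and 4% is a valid bound for every rate up to it. It would be wrong to say that 4% holds only at exactly 25%. But 6.1.2 derives the threshold from the historical sentence, so that sentence should be accurate.

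**The documented shift is small.** Also true: using 26% moves the risk only from 0.039 to 0.051. The larger figures rest on assumed rates.

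**Dexamethasone is part of the regimen by design.** Section 6.1.2 makes that choice openly and plans a descriptive conversion summary. The rule classifies the regimen, not CT-011's separate contribution. That is defensible, and I would not override it with a second decision rule.

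**Section 6.3 does not govern the decision.** Section 6.1.2 ties the rule to partial and complete responses after 4 cycles, so a reader who infers that the primary endpoint is wholly unsettled goes too far. The contradiction between the two sections remains.

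**Conclusion.** The stated basis for the 25% null is unclear in 6.1.2 and does not match 1.3.1, and no rate in the document is a like-for-like benchmark. The null, the cut-offs and the four operating characteristics can stand. What cannot be claimed is that the 4% limit covers lenalidomide plus optional dexamethasone with inactive CT-011, because the document does not show that this background rate is 25% or lower. If it were 30% or 35%, the false-*promising* risk would be 0.129 or 0.295; these are illustrations, not estimates.

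A reader might infer that the true type I error is far above 4%, for instance by adding 29% of the remaining 75% to the 25%: 0.25 + 0.75 × 0.29 = 46.75%, which gives 0.777. The document does not support that. The 29% includes patients treated after progression, is not tied to 4 cycles, and comes with a count that does not fit. If dexamethasone starts only after 3 cycles, about one cycle remains before the 4-cycle assessment, so large inflation is unlikely. That depends on the start time, on which the protocol is inconsistent.

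The stable-disease wording in 6.3 is a plain contradiction of 6.1.2 and Appendix B, note e.

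**What to change.** 1. **Benchmark sentence.** Check 1.3.1 and 6.1.2 against the cited study. State which response categories the 25% counts and whether it is with or without dexamethasone; otherwise state that 25% is a chosen threshold.
2. **Error rates.** Keep the null, cut-offs and sample size. State that 4% is the bound for true rates of 25% or below. Add the probabilities of *promising* and *not promising* at 26%, 30% and 35%, labelled as assumed background rates. Say that the net direction of any mismatch is unknown.
3. **Response rate in 6.3.** Remove stable disease so that the definition is partial response or better, as in 6.1.2.
4. **Dexamethasone timing.** Reconcile the statements on when it may start: after 3 cycles in the synopsis, 1.5, 2.1, 4.3, 5, 5.3 and 5.4; after 2 cycles in the analysis text of 6.1.2; and a parenthesis in 4.3 that refers to a start after cycle 1-2. Which is intended is for the investigators to settle.
5. **Optional.** Report responses reached before any dexamethasone descriptively, beside the conversion summary already planned, and not as a gate on the *promising* call.

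The cost is wording in a few sections and one short table. No cut-off moves in an open-label trial already at Amendment 6, and no new data are needed.
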